Chairside CAD/CAM restorations are generally delivered with adhesive resin cements. The cement may or not require pre-treatment of the tooth by etching or a bonding agent. This creates potential confusion for a clinician as to what the optimal material selection and treatment process should be. A new adhesive resin cement (Suglue 3/3M) is the latest generation of dual cured resin cements from 3M with the innovation to use different tooth pre-treatment options, self-etch, selective enamel etch, or total etch depending on the type of restoration. This simplifies the selection process for delivery of restorations by minimizing the amount of different materials required.

This investigation will be a longitudinal clinical trial to study the long-term clinical performance of a new adhesive resin cement for chairside CAD/CAM restorations. Lithium disilicate chairside CAD/CAM onlays (IPS emaxCAD/Ivoclar) will be adhesively bonded using a selective enamel etch technique with a new generation universal adhesive based on Scotchbond Universal Adhesive (3M) and a new generation resin adhesive cement based on RelyX Ultimate (3M). Full contour zirconia crowns (3M Chairside Zirconia/3M) will be cemented using a self-adhesive technique with the new generation adhesive cement. All restorations may be followed up to five years of service.

5 Specific Aims

The specific aims of this project are:

1. Evaluate the short-term post-operative sensitivity associated with a self-etching resin cement for adhesive luting of chairside zirconia crowns.
2. Evaluate the short-term post-operative sensitivity associated with the adhesive luting technique for ceramic onlays using a selective enamel etch technique and a universal adhesive and dual cure resin cement.
3. Evaluate the longitudinal clinical performance of lithium disilicate ceramic onlays and full contour zirconia crowns for up to five years of clinical service, for a minimum of 3 years. The onlays and crowns will be evaluated with FDI criteria (Hickel et al., 2007 and 2010) for esthetic properties include surface luster, surface staining, margin staining, color match and translucency; functional properties include anatomical form, material fracture, retention, margin adaptation, occlusal contour and wear, and proximal contact and contour; and biological properties include post-operative sensitivity, recurrence of caries, erosion, abfraction as well as gingival index, and plaque index.

6 Research Plan: Methods and Materials

6.1 Subjects

The patient population will be selected from current patients under clinical treatment at the University of Michigan Dental Clinics. Patients need to volunteer for the study and must sign the informed consent. Patients will be over 18 years of age, of either gender, and of any ethnic background. Each patient should have at least one carious lesion or defective restoration to be restored on a maxillary or mandibular premolar or molar. Each lesion or defective restoration should exhibit sufficient size to extend at least one-half the intercuspal width of the tooth requiring an onlay or full crown restoration. The onlays may contain between one and three cusps on the selected tooth as long as an occlusal margin will be present. All teeth will test vital and be asymptomatic at the beginning of treatment. No more than two restorations will be placed per patient. If a patient presents with more than two acceptable teeth for the study, molar teeth will be included prior to premolar teeth. Exclusion criteria will include:

Devital or sensitive teeth

Teeth diagnosed with symptoms of incomplete tooth fracture

Teeth with prior endodontic treatment of any kind

Teeth with a history of direct or indirect pulp capping procedures

Subjects with uncontrolled bruxism or parafunctional habits

Subject has known allergies to any product used during this study

Subject will not be available for the study duration of 5 years

Subjects with significant untreated dental disease to include periodontitis and rampant caries

Pregnant or lactating women

6.2 Informed Consent

The Health Sciences Institutional Review Board of the University of Michigan must review and approve the investigation protocol. Patients can be recruited to the study as soon as the contract is finalized, and funding is provided. Patients who are eligible for the study will be screened by the Clinical Research Coordinator and fully informed of the nature of the study and the need for long-term availability. Each patient who participates in the study will sign an informed consent agreement and the originals will remain at the University. (A copy is included in the Appendix). [REDACTED]

[figure not shown]
[REDACTED] Patients will also receive free bitewing radiographs at the three-year recall appointment as part of routine, standard of care for monitoring dental restorations. Specific study data is not dependent on the radiographs.

After admission to the study a subject may withdraw at any time for any reason. The right of each subject to withdraw and the right of each subject to confidential treatment of personal data will be respected at all times. The PI will record any subject's withdrawal and the reason(s).

6.3 Study Size

There will be 40 zirconia crowns and 40 ceramic onlays placed. The sample size is according to the international standard represented by the criteria of the American Dental Association (ADA, Council on Scientific Affairs: Acceptance Program Guidelines "Restorative Materials", March 1996). 60 patients will be enrolled in the study.

6.4 Study Overview

6.5 Baseline - Restoration Placement

A pre-operative questionnaire will be completed jointly by the patient, Clinical Research Coordinator, and treating doctor at the restorative appointment (copy enclosed in Appendix). This will establish the baseline information from which to compare the responses at subsequent times. Teeth to be restored will be tested subjectively as described in the Data Collections section to follow. The level of sensitivity will be recorded using a criterion-referenced rating scale. The use of the scale will be explained to the patient prior to beginning the evaluation. A Caries Risk Assessment will be completed for each patient at baseline based on the number of restorations the patient reports having received in the previous 12 months. *Low Caries Risk* will be scored for patients having 0 or 1 restoration placed in the previous 12 months. *Moderate Caries Risk* will be scored for patients having 2 or 3 restorations placed in the previous 12 months. And *High Caries Risk* will be scored for patients having 4 or more restorations placed in the previous 12 months.

Pre-treatment

The shade of the tooth to be restored will be determined prior to tooth preparation with a Classic Shade guide (Vita).

Preparation

All restorative procedures will be performed under standard local anesthesia with no increased risks incurred by patients participating in the study beyond those involved in routine dental treatment. An Isolite System, or similar device, will be used to isolate the tooth for cavity preparation, optical imaging, and cementation of the restorations. An Optragate may also be used to retract tissues during digital imaging.

Onlay Preparation

The occlusal walls of the chairside CAD/CAM onlay preparation will be tapered 10° – 12° from the cavosurface to the pulpal floor to ensure distinct occlusal margins. The flare of the proximal boxes will conform to standard criteria with proximal walls exposed for convenience in finishing the margins. There will be no bevels on margins and all floors and walls will be relatively perpendicular to the cavosurface. Any additional design modifications will be in accord with the unique parameters of the computergraphic design software. The onlay will have a 1.5 mm

minimal thickness in the central fissure and 2.0 mm minimal thickness over functional cusps. If in the judgement of the operator, less than 1.0 mm of dentin thickness remains over the pulp, a glass ionomer base (Vitrebond/3M) may be selectively placed prior to completing the preparation.

Crown Preparation

The occlusal walls of the chairside CAD/CAM crown preparation will be tapered 10° – 12° with the axial-pulpal angles rounded. There will be no bevels on margins. Any additional design modifications will be in accord with the unique parameters of the computergraphic design software. The crown will have an axial thickness of greater than 0.8 mm, 1.0 mm minimal thickness in the central fissure, and 1.5 mm minimal thickness over functional cusps. If in the judgement of the operator, less than 1.0 mm of dentin thickness remains over the pulp, a glass ionomer base (Vitrebond/3M) may be selectively placed prior to completing the preparation.

Restoration Fabrication

The manufacturer's instructions will be strictly adhered to in the imaging, design, and manufacturing of the onlays and crowns using the CEREC system (Dentsply Sirona). Following imaging of the tooth preparation with the CEREC PrimeScan, the onlay or crown will be designed using the CEREC software (5.0). The onlays will be milled from prefabricated blocks of IPS emaxCAD (Ivoclar), a lithium disilicate ceramic. They will be stained, glazed and crystallized per manufacturer's instructions to create the final contour and finished surface. The crowns will be milled from prefabricated blocks of 3M Chairside Zirconia (3M) and then sintered in the SpeedFire oven (Dentsply Sirona) per manufacturers guidelines. The crowns will be hand polished to create the final contour and finished surface prior to restoration delivery.

Crown Cementation

Once the crown is ready is for cementation, the internal surface of the crown will be cleaned with air/water spray and air dried with oil-free air.

All of the zirconia crowns will be cemented with a dual cure resin cement, Suglue 3 (3M). Suglue 3 is the latest generation of dual cure adhesive resin cement based on the previously marketed RelyX Unicem 2/RelyX Ultimate adhesive cement chemistry. The internal surfaces of the zirconia crown will be air abraded with 30 µm aluminum oxide (CoJet sand/3M) at a pressure

of 30 psi to create a uniform, matte surface. The crown will be cleaned with alcohol, rinsed with water, and dried with oil-free air.

The cavity preparation will be thoroughly cleaned with water spray for 10 seconds and dried carefully with care taken to prevent over-drying the preparation leaving a glossy surface to the tooth. Suglue 3 Cement will be injected directly into the crown from the automix syringe. The crown will be inserted to complete seating and the excess cement removed. The crown will be light cured for 10 seconds from the facial, lingual and occlusal for a total cure of 30 seconds.

Onlay Cementation

The PVS replica technique will not be used for the onlays since onlay preparations are not as uniform as crown preparations with inconsistent areas for measurement between onlays. The internal surfaces of the IPS emaxCAD onlays will be etched for 20 seconds with 4.9% hydrofluoric acid gel, rinsed for 20 seconds, and then air dried with oil-free air. ADH-19 will be actively applied (scrubbed) with the disposable applicator to the etched ceramic surface for 20 seconds then lightly air dried until there is no movement and the solvent has evaporated completely.

The cavity preparation will be etched for 20 seconds with 37% phosphoric acid (Scotchbond Universal Etchant/3M), rinsed thoroughly with water, and lightly air dried leaving a moist surface that is glossy in appearance. ADH-19 is the latest generation of universal bonding agents from 3M based on the Scotchbond Universal Adhesive (3M) chemistry. A thin coating of ADH-19 universal bonding agent will be actively applied (scrubbed) with a disposable applicator and air dried until there is no movement and the solvent has completely evaporated. Suglue 3 Cement will be injected directly into the tooth preparation from the automix syringe. The onlay will be inserted into the cement to complete seating and the excess cement removed. All onlays will be light cured for 10 seconds from the facial, lingual and occlusal for a total cure of 30 seconds.

Finishing and polishing will be initiated after visible light curing of the luting agent. A series of diamond finishing burs, rubber abrasive points and cups, finishing strips, and diamond polishing pastes will be used for removal of excess cement, final contouring of the restoration, and adjustment of the occlusion.

7 Data Collection

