7.1 Post-Operative Sensitivity

To evaluate the immediate post-operative sensitivity, patients will be contacted by telephone once a week after the initial appointment for four weeks or until the restoration is reported asymptomatic. A criterion-referenced rating scale will be used to measure sensitivity. The phone interview will be used as a follow-up procedure to minimize recall loss as the patient is not required to return to the clinic. During the phone interview a criterion-referenced rating will be made of functional tooth sensitivity using the following scale. Patients will only be asked to return for an evaluation if they are having continued discomfort or any indication of premature occlusal contact.

Sensitivity Criteria:

- 1= No sensitivity is experienced at anytime
- 2= Slight sensitivity is experienced occasionally but it is not uncomfortable
- 3= Moderate sensitivity is experienced occasionally, and it is noticeably uncomfortable
- 4= Severe discomfort is noted routinely with cold or pressure stimulation

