In case of occurrence of any Adverse Event or Adverse Device Effect the appropriate form provided by 3M has to be filled in by the investigator. In case of any near incident or any event that could lead or led to any medical hazard for the investigator (user) of the investigational device the Incident/Near Incident form provided by the sponsor has to be filled in by the investigator.

Any adverse reactions to the treatment provided as part of the study will be fully investigated and recorded on the Adverse Event/Adverse Device Effect form (See Appendix), including details of the appropriate clinical action taken. An adverse event is defined as any unintended adverse experience associated with the study materials or study procedures that results in an unplanned medical assessment or treatment or changes the risk to subjects.

Restoration Failures

If a crown or onlay fails during the term of the study, the investigator will provide complete information on the manner of the failure and the proposed resolution to the study contact person at 3M. Failures associated with the bonding agent, cement, crowns and onlays that may be expected in this study include:

- loosening or complete loss of the crown or onlay

- fracture and/or chipping of the crown or onlay
- surface roughening or discoloration of the crown or onlay

Upon a determination that the crown or onlay failure did not result from other identifiable causes, and with 3M's prior approval, the Institution will make arrangements to replace the crown or onlay or carry out appropriate alternative treatment (i.e. replacement with a fixed or removable partial denture) at 3M's expense. 3M will not be responsible for any expenses incurred without its prior approval. If a crown or onlay fails after the term of the study, 3M will not be responsible for any costs incurred in its repair or replacement. 3M will have no responsibility for any other treatment a patient may receive during the term of the study or after the study has ended.

Monitoring

Monitoring visits will take place at the study center. During these visits, questions on the study conduct will be discussed and the study documentation will be reviewed. The study monitor will check whether the Clinical Investigation Plan was followed and whether the investigational device was applied according to the Instructions for use. The monitor will verify if appropriate patient consent is available for each patient and that it was included before enrolment.

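### The onlays are assigned to selective enamel etching, but the only tooth-etching instruction does not limit the acid to enamel

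*Combined protocol and SAP*

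**What the plan says.** The study description, before Section 5, presents the new cement as compatible with "different tooth pre-treatment options, self-etch, selective enamel etch, or total etch depending on the type of restoration". These are three separate options. It then assigns the onlays to one of them: "Lithium disilicate chairside CAD/CAM onlays (IPS emaxCAD/Ivoclar) will be adhesively bonded using a selective enamel etch technique". Specific Aim 2 in Section 5 repeats the assignment. It sets out to evaluate short-term post-operative sensitivity for the "adhesive luting technique for ceramic onlays using a selective enamel etch technique and a universal adhesive and dual cure resin cement".

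The step-by-step procedure is in Section 6.5 under Onlay Cementation. It has two etching steps. The first treats the ceramic: "The internal surfaces of the IPS emaxCAD onlays will be etched for 20 seconds with 4.9% hydrofluoric acid gel". The second treats the tooth: "The cavity preparation will be etched for 20 seconds with 37% phosphoric acid (Scotchbond Universal Etchant/3M), rinsed thoroughly with water". The bonding agent and cement follow.

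The outcome for Aim 2 is described in Section 7.1. Patients are telephoned weekly for up to four weeks: "During the phone interview a criterion-referenced rating will be made of functional tooth sensitivity using the following scale". The scale runs from 1 to 4.

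**The concern.** Aim 2 concerns a named luting technique, and the place where the acid is applied is part of what defines that technique. The aims name one etch mode, while the operating instruction, read as written, describes something wider. If operators follow the instruction, the four-week sensitivity ratings will belong to onlays whose dentin may have been acid-etched, yet the report will call the technique selective enamel etch. If some operators follow Section 6.5 and others follow the study description, the onlay group will be a mixture under a single label. In both cases the onlay result would not answer Aim 2 as worded.

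Monitoring does not settle the matter. Under Section 7.3 the monitor checks that the Clinical Investigation Plan was followed and "whether the investigational device was applied according to the Instructions for use". The plan points both ways: etching enamel only departs from the wording of Section 6.5, and etching the whole preparation departs from the study description and Aim 2.

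**Working it through.** The point involves no sample size, error rate or event count, so the check is a comparison of texts.

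**1. Where the technique is named.** In the study description and Section 5 together, selective enamel etch occurs 3 times: once in the list of options and twice assigning the onlays to it (study description and Aim 2). Total etch occurs once, in the list, as a different option.

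**2. Where the technique is carried out.** Section 6.5 runs from the baseline questionnaire through preparation, fabrication and cementation. It contains the word enamel 0 times. Under Onlay Cementation there are 2 etching steps, of which 1 is on the ceramic, so 2 − 1 = 1 step etches the tooth. The crown procedure has no acid etch of the tooth. The adverse event record in the Appendix lists the etchant by product name only.

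| | Study description and Aim 2 | Section 6.5, Onlay Cementation |
|---|---|---|
| Technique named | Selective enamel etch (2 assignments) | None |
| Surface to be acid-etched on the tooth | Enamel, by the name of the technique | The cavity preparation, without restriction |
| Instruction to keep acid off dentin | Implied by the name | Absent |

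**3. Whether *cavity preparation* can be read as enamel only.** The same term is used in the crown procedure for what is cleaned with water spray before cementation, and nothing there limits it to part of the tooth. The onlay text also names a particular surface when it means one, as in the hydrofluoric acid step. The plain reading is therefore the preparation as a whole.

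**4. Whether the difference can arise in practice.** The onlay preparation has a pulpal floor, and Section 6.5 allows a glass ionomer base if "less than 1.0 mm of dentin thickness remains over the pulp". This shows that dentin can be part of the preparation. It does not show how much dentin is exposed when the acid is applied.

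**5. Reach.** Section 6.3 plans 40 onlays, and the single tooth-etching sentence is the written instruction for all of them. That is the reach of the sentence, not a count of teeth etched differently from Aim 2.

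**The case against.** The strongest reply is that a qualifier is missing and no wrong instruction has been shown. Section 6.5 never mentions total etch and never directs the operator to etch dentin. The study description names the technique, and Section 6.5 supplies the agent, concentration and time. Read together, the named technique could govern where the acid goes. The direction to leave the tooth glossy does not identify total etch either, because the crown procedure asks for a glossy surface with no acid etch. The Instructions for use may define the step, and they are not among the documents. Finally, crowns and onlays are analysed separately, no etch techniques are compared, and the harm depends on operators reading the step literally.

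Much of this stands. The intended technique is unknown, the Instructions for use might resolve it, and no effect on sensitivity can be sized. It does not remove the inconsistency. Section 6.5 is the detailed procedure, with times, concentrations and products, and an operator should not have to override its wording by recalling the introduction. The harmonising reading itself concedes that the step cannot be carried out correctly from its own text.

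One practical objection also stands. None of the forms reproduced in the Appendix has a field for where the etchant was applied, so for any onlay already placed the technique may have to be established from other records or from the operator. That limits retrospective labelling but does not affect the main correction.

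**Conclusion.** The concern holds. The study description and Aim 2 assign the onlays to selective enamel etching, and the one operative sentence, covering all 40 planned onlays, does not restrict the acid to enamel. Confidence is high for the mismatch in the text. No claim is made about what operators will do or have done.

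What is at risk is the name of the technique to which the onlay conclusion is attached, above all the Aim 2 sensitivity result. That risk assumes that at least some operators follow Section 6.5 literally and that dentin is exposed in at least some preparations. The sample size, the Kaplan-Meier primary analysis and the planned tests do not depend on the point. It should be fixed.

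**What to change.** If selective enamel etch is intended, amend the tooth-etching sentence in Section 6.5 (Onlay Cementation) so that the phosphoric acid is applied to the enamel of the preparation only, with time, concentration and product unchanged. If total etch is intended, leave that sentence and rename the technique in the study description and in Aim 2.

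Under either choice, report onlay results under the technique actually used, including any onlays placed before the amendment. Because the reproduced forms do not record where the etchant was applied, a short entry on the etched surface in the placement record would support this for later onlays. For earlier ones the basis for the classification should be stated.

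The first option costs one sentence; the second costs edits in two places. Either goes through the Amendment Form with approval by the principal investigator, the sponsor and the IRB. The added placement entry is optional and costs one item on a form. Sample size, visits and analysis do not change.
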